9.2.1. Dose Interruption Safety Criteria and Management

Patients who experience hematologic adverse events as described in [Table 3](#), significant clinical laboratory abnormality, or adverse events that may reflect an unfavorable risk-benefit profile may have their dose interrupted at the discretion of the Investigator. The Medical Monitor(s) should be consulted whenever possible prior to decisions for dose interruption.

Patients who withdraw consent and therefore are discontinued from the study should undergo an **Early Termination Visit** and associated adverse events should be followed as described in [Section 11](#) Adverse Events.

Hematology parameters will be assessed bi-weekly for the first 4 weeks of the Treatment Period, and every 4 weeks thereafter for the remainder of the study. Prior to dose interruption, hematology parameters should be confirmed with repeat testing at an **Unscheduled Visit** within 72 hours, except in severe cases (i.e.: neutrophil counts below $0.5 \times 10^9/L$) where immediate interruption of dosing is necessary for the safety of the patient. **Blood draws confirming dose interruption criteria should occur prior to the first daily dose on the day of draw.**

Dose interruption requirements for hematologic abnormalities are provided below. However, less significant changes may warrant clinical intervention and the Investigator should use his/her best clinical judgment when considering a dose interruption whether for singular or aggregate hematology results above the limits provided in Table 3, or for other clinical signs, symptoms, or considerations that suggest dose interruption is in the best interest of the patient.

Table 3: Selected Hematologic Thresholds for Dose Interruption

Neutrophil Count	Dose Adjustment
Between 0.5 to 1 x 10 ⁹ /L (Grade 3)	Interrupt dose until recovered to greater than 1.5 x 10 ⁹ /L and resume dosing at previous dose
Less than 0.5 x 10 ⁹ /L (Grade 4)	Severe case: Interrupt dose immediately and repeat CBC with differential within 72 hours. Recommend hematology consult and contact medical monitor. Permanent discontinuation of treatment should occur upon repeat confirmation of value
Female Hemoglobin Level	Dose Adjustment
Less than 10 g/dL	Interrupt dose until recovered to greater than 10.5 g/dL and resume dosing at previous dose
Male Hemoglobin Level	Dose Adjustment
Less than 11.5 g/dL	Interrupt dose until recovered to greater than 12 g/dL and resume dosing at previous dose

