Platelet Count	Dose Adjustment
Less than 75 x 10 ⁹ /L	Interrupt dose until recovered to greater than 100 x 10 ⁹ /L and resume dosing at previous dose
Greater than 750 x 10 ⁹ /L	Interrupt dose until recovered to less than 600 x 10 ⁹ /L and resume dosing as prescribed by the Investigator

Upon dose interruption, the parameters that triggered the interruption should be monitored at least weekly until either: 1) recovery above the threshold for dosing resumption is achieved, or 2) a 21-day dose interruption period has elapsed, at which time a discussion between the PI and the Medical Monitor should occur to evaluate whether or not the subject should discontinue treatment permanently. In the case of severe neutropenia (neutrophil counts less than 0.5 x 10⁹/L) patient should interrupt dose **immediately** and repeat CBC with differential within 72 hours. The Medical Monitor should be contacted and a hematology consult should be made if appropriate. Permanent discontinuation of treatment should occur upon repeat confirmation of value. Patients who discontinue treatment due to lack of acceptable recovery of parameters should continue to be followed for all safety and efficacy assessments through the completion of the 24-week treatment period, and will have all endpoints (including efficacy) collected accordingly.

Subjects with both a positive SARS-CoV-2 test (antigen or antibody) AND signs or symptoms consistent with SARS-CoV-2 infection should immediately interrupt dosing with study drug. Dose interruption should continue until symptoms subside (it is not necessary to have a negative SARS-CoV-2 test result). If symptoms do not subside within a 21-day dose interruption period, a discussion between the PI and the Medical Monitor should occur to evaluate whether or not the

subject should discontinue treatment permanently. Signs and symptoms include, but are not limited to: fever or chills, cough, shortness of breath or difficulty breathing, fatigue, muscle or body aches, headache, new loss of taste or smell, sore throat, congestion or runny nose, nausea or vomiting, diarrhea, trouble breathing, persistent pain or pressure in the chest, new confusion, inability to wake or stay awake, bluish lips or face.

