Subjects who have signs or symptoms consistent with SARS-CoV-2 infection should be tested for SARS-CoV-2 and do not have to dose interrupt unless the test result is positive. Subjects who have a positive SARS-CoV-2 test (antigen or antibody) but do not have any signs or symptoms consistent with SARS-CoV-2 infection are not required to dose interrupt.

Table 4: SARS-CoV-2 Dose Interruption Criteria

SARS-CoV-2 Test Result	SARS-CoV-2 Symptoms	Dose Interruption
Positive	Yes	Yes
Positive	No	No
Negative	Yes	No

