9.5. Concomitant Medications and Procedures

All medications, including over-the-counter therapies (e.g., vitamins, herbal, and nutritional supplements) and vaccinations (including the SARS-CoV-2 vaccination), taken at the time of the Screening Visit through the Follow-Up Visit will be recorded in the patient's source documentation and documented in the eCRF. Additionally, any prior janus kinase (JAK) inhibitor use or live virus vaccinations (including Herpes Zoster) will be recorded.

To date, there is no clear evidence of any safety concern for receipt of a SARS-CoV-2 vaccine during the treatment period. Existing data on JAK inhibitors and vaccines, including the SARS-CoV-2 vaccine, are insufficient to conclude whether JAK inhibitors, including CTP-543, have an effect on vaccine effectiveness, though data to date do not suggest that a major effect is likely. Subjects considering enrollment in the CP543.3001 trial may wish to receive their vaccine(s) before entering the trial. As subject and public health are paramount, SARS-CoV-2 vaccination should not be delayed or withheld for subjects already enrolled in the CTP-543 trial.

Knowledge about the vaccines and virus is continually growing. The Sponsor or [REDACTED] will notify sites as new information is obtained that might further inform vaccine-related questions during the study. Please also carefully read the product information (package insert) for the vaccine being used, noting any specific precautions or warnings for concomitant administration with JAK inhibitors or immunosuppressants.

Any concomitant medication deemed necessary for the wellbeing of the patient may be given at the discretion of the Investigator. Use of medications that are prohibited per protocol will require patient withdrawal from the study. However, under certain circumstances, and in consultation with the Medical Monitor, short-term use of a prohibited medication may not necessitate withdrawal when its use is unlikely to unfavorably alter the risk-benefit of subject participation or confound the study endpoints.

The following treatments are not permitted during the study:

- Medications that may affect hair regrowth or immune response (such as: corticosteroids administered orally, by injection, or applied to areas of skin affected by alopecia; platelet-rich injections; topical application to affected areas of anthralin, squaric acid, diphenylcyclopropenone, or minoxidil;

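### Protocol 9.2.1 lets an antibody result decide dose interruption in a patient with COVID-19-like symptoms, although it does not establish current infection (minor; cheap to correct)

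*Protocol*

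**What the plan says.** The operative rule, in Protocol Section 9.2.1, is: "Subjects with both a positive SARS-CoV-2 test (antigen or antibody) AND signs or symptoms consistent with SARS-CoV-2 infection should immediately interrupt dosing". For patients with symptoms and no result yet, the section says that they "should be tested for SARS-CoV-2 and do not have to dose interrupt unless the test result is positive"; that sentence names no type of test. The rule for patients without symptoms uses the same parenthesis: "Subjects who have a positive SARS-CoV-2 test (antigen or antibody) but do not have any signs or symptoms" are not required to interrupt. Table 4 has a single result column. Positive with symptoms maps to interruption; positive without symptoms and negative with symptoms do not.

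On duration: "Dose interruption should continue until symptoms subside (it is not necessary to have a negative SARS-CoV-2 test result"). If symptoms last 21 days, the investigator and the Medical Monitor discuss whether treatment should end.

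On vaccination, Section 9.5 says "Subjects considering enrollment in the CP543.3001 trial may wish to receive their vaccine(s) before entering the trial" and "SARS-CoV-2 vaccination should not be delayed or withheld for subjects already enrolled in the CTP-543 trial". Section 10.1 asks sites to probe for earlier SARS-CoV-2 infection, and exclusion criterion 11 (Section 8.2) removes only patients with a positive test in the 2 weeks before Baseline.

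There is some discretion. Section 9.2 leaves interruption for intolerability to the investigator's judgement in consultation with the Medical Monitor. Section 9.2.1 adds: "The Medical Monitor(s) should be consulted whenever possible prior to decisions for dose interruption". It also lets the investigator interrupt "for other clinical signs, symptoms, or considerations that suggest dose interruption is in the best interest of the patient".

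**The concern.** Symptoms alone do not stop drug under this rule; the test result decides. That test therefore needs to show whether the patient is infected now. An antigen test is directed at that question. An antibody test is not: it reflects an immune response, which can follow vaccination or a past infection and can be absent early in a new one.

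The rule can thus err both ways. It can take an uninfected patient off drug, and it can give a site a stated reason not to interrupt in a patient who is infected. What is at stake is a few days of exposure for some patients, some extra entries in the interruption summaries, and the soundness of a written safety instruction.

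**Working it through.** The plan gives no figure on this point, so there is none to reproduce. The check is a reading of the text plus a small calculation.

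**1. Is the antibody wording current and deliberate?** It stands in the body of Section 9.2.1, not only in the amendment log. It appears twice, once for symptomatic and once for asymptomatic patients. Table 4 does not separate test types. No sentence sets aside antibody positivity after vaccination or past infection, and none asks for a confirmatory test. For hematology, by contrast, the same section asks for repeat confirmation before interruption except in severe cases.

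**2. Can an uninfected study patient be antibody-positive?** Section 9.5 favours vaccination before and during the trial, and exclusion criterion 11 looks back only 2 weeks, so patients with an earlier immune response can be enrolled. That such a patient tests positive is general knowledge and is not stated in the documents. For vaccination it also depends on the assay, which is not named.

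**3. Is the symptom requirement a strong filter?** The list in Section 9.2.1 has 16 entries, is open-ended and sets no minimum number. Section 11.1 gives three examples of vaccine reactions (fever, fatigue, headache), and all 3 of 3 are on the list.

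**4. What does the rule direct?**

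| Symptomatic patient | Possible antibody result | Table 4 outcome | Outcome the rule intends |
|---|---|---|---|
| Vaccinated or previously infected, not infected now | Positive | Interrupt | Continue |
| Early in a current infection | Negative | No interruption | Interrupt |

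**5. How often?** SARS-CoV-2 tests scheduled in Protocol Table 2: 0. Listed in Appendix 17.1: 0. The case arises only if a site chooses an antibody test for a symptomatic patient, and the documents give no rate for that.

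**6. How much drug is lost per unnecessary stop?**

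- Scheduled doses: 24 weeks × 7 days × 2 per day = 336.
- Doses lost: 2 × days of interruption. The stop ends with the symptoms, so its length is the symptom duration, for which 1 to 7 days is an assumption.
- 1 day: 2/336 = 0.6%.
- 7 days: 14/336 = 4.2%.
- 21 days, the protocol's discussion point: 42/336 = 12.5%. This would need three weeks of unbroken symptoms, and the documents give no basis for expecting that in an uninfected patient.

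**The case against.** The strongest reply is that this is a brief precaution in patients taking a drug with potential immunosuppressive properties (Section 10.1), and that clinicians stay in control. The symptoms must be judged consistent with SARS-CoV-2 infection, Section 9.2 refers to investigator judgement with the Medical Monitor, and consultation is asked for whenever possible. Lasting antibody positivity cannot prolong a stop, because no negative test is needed to resume. The chain to harm (site choice, assay, past exposure, unrelated symptom) has no frequency at any link.

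Most of this stands, and it limits the size of the point. It does not make the wording right. The symptomatic rule is directive, Table 4 says yes, and the contrasting asymptomatic case is expressly not required. The judgement in Section 9.2 concerns intolerability and refers to Section 9.2.1 for the details, so it softens the specific instruction without cancelling it. Nor is the rule consistently precautionary, since a symptomatic patient need not stop until a test is positive. The error in the other direction is largely covered: a negative result means only that the patient does not have to interrupt, the investigator may still do so on clinical grounds, and Section 8.3 ends treatment for a serious adverse event associated with SARS-CoV-2 infection.

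Reporting is also partly protected. SAP Section 9.2 would count an unnecessary stop as a dose interruption, but it allows free-text reasons to be reviewed before database lock, and SAP Section 11 lists dosing exceptions related to COVID-19.

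**Conclusion.** The point holds as a minor flaw in a stated safety rule: Section 9.2.1 accepts, for a decision about current infection, a test that does not establish it. Each unnecessary stop costs an assumed 0.6% to 4.2% of scheduled doses. The number of patients affected cannot be estimated. The conclusion assumes that at least one site uses an antibody test for symptomatic patients and, for vaccinated patients, that the assay responds to vaccination.

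A reader might infer more, and the documents do not support it:

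- *That the primary result is at risk.* The rule is the same in all blinded arms, and Protocol Section 12.4.2 applies a treatment-policy strategy to temporary as well as permanent stops.
- *That unnecessary stops could prompt an unscheduled DMC review.* Section 8.5 names a high frequency of interruptions as a possible trigger, but no frequency can be derived here.
- *That antibody-based stops can be separated in the data because SAP Appendix 15.4 has its own term for a positive antibody test.* That appendix is a MedDRA query list for classifying adverse events. It does not show that the type of test behind an interruption is recorded.
- *That the investigator has no latitude.* Sections 9.2 and 9.2.1 give some, as set out above.

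**What to change.** In Section 9.2.1:

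- Symptomatic rule: change the parenthesis to *(antigen or nucleic acid, taken for the current symptom episode)*.
- Testing sentence: name the same test types.
- Asymptomatic rule: change the parenthesis to *(antigen or nucleic acid)*.
- Table 4: add the same qualifier to the heading of the test-result column.
- Add: *An antibody result alone neither triggers interruption nor rules out infection; the Investigator may hold dosing on clinical judgment while an antigen or nucleic-acid result is obtained.* The last clause supplies an interim rule for sites that cannot get the result at once.

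Exclusion criterion 11 can stay as it is. The cost is three edited sentences, one added sentence and one column heading. Testing of symptomatic patients is already required, so no scheduled test or visit is added. The downside is that a site with only antibody tests must obtain an antigen or nucleic-acid test for its symptomatic patients.

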9.3. Treatment Compliance

At each scheduled study visit after randomization, the Investigator or designee will interview the patient regarding treatment compliance and compare the number of dispensed versus returned study drug tablets. Patients should strive for 100% compliance with the daily dosing schedule. Retraining on treatment compliance should occur for patients with less than 80% compliance at any visit and the Sponsor should be notified.

9.4. Study Drug Materials and Management

Please consult the Pharmacy Manual for a complete description of the study drug and requirements for storage, handling, dispensing, accountability, returns and destruction.

9.4.1. Physical Description of Study Drug

Study drug will include CTP-543 and matching placebo. Details regarding formulation and dosage are presented in [Table 5](#).

Table 5: Investigational Product

	Investigational Product (CTP-543 or Placebo)
Product Name:	CTP-543 or Matching placebo
Dosage Form:	Tablet
Dosage Strength of CTP-543	8 mg, 12 mg
Route of Administration	Oral
Physical Description	White, capsule-shaped tablets

9.4.2. Study Drug Packaging, Labeling, and Storage

Study drug will be packaged and labeled by an appropriately qualified vendor. Each patient will receive one 60 count bottle of study medication at each 4-week study visit. Details of the packaging, labeling and dispensing instructions can be found in the Pharmacy Manual.

The label(s) for the investigational product and placebo will include the required caution statements and/or regulatory statements, as applicable per local regulations.

Adequate supplies of study drug will be provided to each site by the sponsor or designee. Study drug should be stored in the original container between 15°C to 25°C (59°F to 77°F), as stated on the product label, in a secure, temperature-monitored, locked area, under the responsibility of the Investigator or other authorized individual until dispensed to the patients.

Study drug dispensed to patients should be stored in the original bottle at room temperature as stated on the package label. No special handling procedures are required. Due to the COVID-19 pandemic, Direct to Patient (DTP) shipping services may be warranted in cases where a patient is not able to attend in clinic visits or a site is closed. Additional information can be found in the Pharmacy Manual.

9.4.3. Study Drug Preparation and Administration

No study drug preparation is required. Patients will take the first dose of study drug in the clinic on Day 1 and will be instructed to take study drug approximately every 12 hours for the duration of the Treatment Period. Patients should dose study drug in the clinic on all Study Visit Days after clinical laboratory blood draws are completed.

Study drug should be taken at approximately the same times each day, with water, and without regard to food. Patients should be instructed to take one tablet in the morning and one tablet in the evening, approximately 12 hours apart. If a dose is missed, the patient should skip the missed dose and resume dosing at the next scheduled dose. The patient should not take two doses at the same time. Deviations from prescribed dosing should be discussed at each visit for assessment of compliance and retraining when necessary.

9.4.4. Study Drug Return and Disposal

The Sponsor (or designee) will review with the Investigator and relevant site personnel the process for study treatment return, disposal, and/or destruction, including responsibilities for the site versus the Sponsor (or designee). Specific requirements for destruction or return are defined in the Pharmacy Manual.

9.4.5. Study Drug Accountability

To satisfy regulatory requirements regarding drug accountability, all study drug will be reconciled in full. The Investigator or designee must maintain accurate records of the receipt of study drug, including date received, lot number, amount received, condition of the package, and the disposition of study drug.

Current dispensing records will also be maintained, including the date and amount of medication dispensed to each individual patient. Returned study drug records will be maintained and final study drug reconciliation will also be recorded for each patient.

9.5. Concomitant Medications and Procedures

All medications, including over-the-counter therapies (e.g., vitamins, herbal, and nutritional supplements) and vaccinations (including the SARS-CoV-2 vaccination), taken at the time of the Screening Visit through the Follow-Up Visit will be recorded in the patient's source documentation and documented in the eCRF. Additionally, any prior janus kinase (JAK) inhibitor use or live virus vaccinations (including Herpes Zoster) will be recorded.

To date, there is no clear evidence of any safety concern for receipt of a SARS-CoV-2 vaccine during the treatment period. Existing data on JAK inhibitors and vaccines, including the SARS-CoV-2 vaccine, are insufficient to conclude whether JAK inhibitors, including CTP-543, have an effect on vaccine effectiveness, though data to date do not suggest that a major effect is likely. Subjects considering enrollment in the CP543.3001 trial may wish to receive their vaccine(s) before entering the trial. As subject and public health are paramount, SARS-CoV-2 vaccination should not be delayed or withheld for subjects already enrolled in the CTP-543 trial.

Knowledge about the vaccines and virus is continually growing. The Sponsor or [REDACTED] will notify sites as new information is obtained that might further inform vaccine-related questions during the study. Please also carefully read the product information (package insert) for the vaccine being used, noting any specific precautions or warnings for concomitant administration with JAK inhibitors or immunosuppressants.

Any concomitant medication deemed necessary for the wellbeing of the patient may be given at the discretion of the Investigator. Use of medications that are prohibited per protocol will require patient withdrawal from the study. However, under certain circumstances, and in consultation with the Medical Monitor, short-term use of a prohibited medication may not necessitate withdrawal when its use is unlikely to unfavorably alter the risk-benefit of subject participation or confound the study endpoints.

The following treatments are not permitted during the study:

- Medications that may affect hair regrowth or immune response (such as: corticosteroids administered orally, by injection, or applied to areas of skin affected by alopecia; platelet-rich injections; topical application to affected areas of anthralin, squaric acid, diphenylcyclopropenone, or minoxidil;
- Chronic or long-term treatment with systemic immunosuppressive medications including but not limited to methotrexate, cyclosporine, and azathioprine; chloroquine derivatives; Janus kinase inhibitors (ruxolitinib, tofacitinib, etc), etanercept; or biologics (adalimumab, atlizumab, canakinumab, certolizumab, fontolizumab, golimumab, infliximab, mepolizumab, rituximab, secukinumab, tocilizumab, ustekinumab);
 - NOTE: a short course of steroid treatment for acute treatment of a condition during the trial may be allowed following discussion with the Medical Monitor
- Use of strong CYP3A4 inhibitors (such as, but not limited to clarithromycin, conivaptan, grapefruit juice, indinavir, itraconazole, ketoconazole, lopinavir/ritonavir, mibefradil, nefazodone, nelfinavir, posaconazole, saquinavir, telaprevir, telithromycin, voriconazole, or fluconazole) dosed for systemic exposure;

- Use of strong CYP3A4 inducers (such as, but not limited to barbiturates, carbamazepine, efavirenz, glucocorticoids, modafinil, nevirapine, oxcarbazepine, phenobarbital, phenytoin, pioglitazone, rifabutin, rifampin, St. John's Wort, or troglitazone) dosed for systemic exposure.
- Live vaccines including (but are not limited to) the measles, mumps, and rubella (MMR) vaccine; intranasal flu vaccine; and Zostavax (but not Shingrix) for herpes zoster.

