8.3. Patient Withdrawal Criteria

For all patients, it is the intent that patients who discontinue study medication (at any time) for any reason will continue to be followed for all protocol-planned study visits through the completion of the 24-week treatment period, and will have all endpoints (including efficacy) collected accordingly.

The Investigator, Sponsor, or its designee may decide a patient should discontinue treatment at any time and for any reason. In addition, patients will discontinue randomized treatment if they:

- Experience an intolerable adverse event, including but not limited to bone marrow related events characterized by protocol specified hematologic abnormalities, or a \geq Grade 3 cardiac event, or a \geq Grade 4 (other) adverse event (CTCAE v5.0 criteria) considered possibly related to study drug. Because laboratory abnormalities can occasionally occur that do not in themselves pose an unacceptable risk to subject safety (e.g., CK elevations with exercise, laboratory errors or artifacts), the occurrence of a \geq Grade 4 laboratory abnormality, or any laboratory abnormality of concern to the Investigator, will be discussed with the Medical Monitor and a determination will be made, based on a reassessment of risk-benefit for the subject, whether the subject should discontinue randomized treatment. Documentation on the determination will be maintained in the study files;
- Require a medication that is prohibited by the protocol. However, under certain circumstances, and in consultation with the Medical Monitor, short-term use of a prohibited medication may not necessitate withdrawal of treatment when its use is unlikely to unfavorably alter the risk-benefit of subject participation;
- In the opinion of the Investigator, have any medically appropriate reason;
- Become pregnant;
- Have a serious adverse event associated with a SARS-CoV-2 infection;

- The Investigator believes that further treatment is undesirable or the risk-benefit profile has become unfavorable.

Furthermore, dose interruptions lasting more than 21 days may require treatment discontinuation on a case by case basis following consultation with the Medical Monitor.

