12.4.2. Efficacy

The primary analysis targets an effect of treatment (response rates at 24 weeks) among subjects given the opportunity for treatment who are dispensed study drug. The treatment policy strategy is used for the intercurrent event of discontinuation of study treatment (either temporarily or permanently) and so the response rates at 24 weeks are of interest, irrespective of continued therapy, in line with the intent-to-treat principle.

For the primary efficacy analysis and the key secondary efficacy analysis, a 0.025 (two-sided) alpha-level will be allocated to each dose for comparison with placebo to adjust for multiplicity of testing associated with two doses. Additional secondary endpoints will be tested in the following order (see Section 12.4.3) and be considered statistically significant and alpha-level protected if they (and all prior endpoints in the hierarchy for that dose versus placebo) achieve statistical significance at the 0.025 level of significance. Irrespective, nominal p-values will be provided. Testing will be performed only for the Treatment Period. Missing values will be handled as specified in Section [12.4.4](#).

Primary Efficacy Endpoint

The primary efficacy endpoint will be the proportion of patients achieving an absolute SALT score ≤ 20 at Week 24. Pairwise treatment group differences from placebo will be assessed with the Cochran-Mantel-Haenszel test using baseline scalp hair loss (partial vs complete/near-complete) as the stratification factor, for each active treatment group versus placebo.

Other Efficacy Endpoints

[figure not shown]
For proportions of patients achieving specified improvement criteria (eg, CGI-I and PGI-I responders), pairwise treatment group differences from placebo at each scheduled evaluation will be assessed with the Cochran-Mantel-Haenszel test using baseline scalp hair loss as the stratification factor.

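### Section 9.5 takes patients who use prohibited medication out of the study; Section 8.3 only stops their treatment and intends follow-up to Week 24

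*Protocol*

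**What the plan says.** **Protocol Section 9.5** sets the rule that "Use of medications that are prohibited per protocol will require patient withdrawal from the study". It allows an exception, in consultation with the Medical Monitor, for short-term use when "its use is unlikely to unfavorably alter the risk-benefit of subject participation or confound the study endpoints".

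**Protocol Section 8.3** deals with the same event differently. Under the lead-in "patients will discontinue randomized treatment if they" it lists "Require a medication that is prohibited by the protocol". Its own exception says that "short-term use of a prohibited medication may not necessitate withdrawal of treatment". The section opens by stating an aim: "patients who discontinue study medication (at any time) for any reason will continue to be followed for all protocol-planned study visits". This follow-up is meant to last until Week 24 and to include the efficacy endpoints. The one ground on which 8.3 says the investigator must take a patient out of the study is withdrawal of consent.

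**Protocol Section 12.4.2** applies a treatment policy strategy to stopping study treatment, whether temporary or permanent.

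**SAP Section 8.2.1** keeps SALT scores obtained after treatment discontinuation, provided the patient is still on study. It imputes missing SALT scores under a missing-at-random (MAR) assumption, separately by arm. **SAP Section 8.3.1** handles missing SPRO scores in a similar way.

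**The concern.** One event has two consequences. Under 8.3 the patient stops drug and keeps attending; under 9.5 the patient leaves. For use outside the exception, a site that applies 9.5 defeats the follow-up that 8.3 intends, and different sites may choose differently.

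At stake are observed Week 24 SALT and SPRO values. The primary analysis wants outcomes regardless of continued therapy, and 9.5 turns some of them into missing values. The plan recovers them only in part:

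- **Early termination visit.** SAP Section 8.1.2 (Table 2) assigns such a visit to Week 24 for efficacy only if it falls on Days 166 to 172.
- **Sensitivity 1 (SAP Section 8.2.3).** Placebo-based imputation applies only to study discontinuation for a treatment-emergent adverse event or lack of efficacy, and those reasons are collected as sub-reasons of withdrawn consent. A withdrawal imposed by 9.5 falls among the other reasons and is imputed from the patient's own arm.
- **Tipping point (SAP Section 8.2.3).** This adjusts all imputed SALT values, so it gives partial cover for the primary endpoint. It is run for a dose only if the primary result for that dose is significant.
- **SPRO at Week 24.** This is the first key secondary endpoint and is alpha-controlled. The sensitivity analyses are specified for the primary endpoint, so none covers it.

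**Working it through.** **Step 1. The texts side by side**

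| | Section 9.5 | Section 8.3 |
|---|---|---|
| Event | use of a prohibited medication | requiring a prohibited medication |
| Consequence | leaves the study | stops randomized treatment |
| Exception | short-term use, Medical Monitor consulted, endpoints not confounded | short-term use, Medical Monitor consulted; worded as withdrawal of treatment |
| Follow-up | none stated | intended through Week 24, all endpoints |

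The one section says use and the other says require, but in practice this is the same event. Other parts of the protocol (Synopsis, Sections 7.1 and 9.2.1) also keep patients who stop treatment under assessment. No text reconciles 9.5 with them.

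**Step 2. The plan's power figures**

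Inputs from Protocol Section 12.1: response 40%, 25% and 10%; n = 210, 350 and 140 (12 mg, 8 mg, placebo); two-sided alpha 0.025. Pooled-variance chi-square approximation, 8 mg versus placebo:

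- pooled rate = (350 x 0.25 + 140 x 0.10)/490 = 0.2071
- null SE = sqrt(0.2071 x 0.7929 x (1/350 + 1/140)) = 0.0405
- alternative SE = sqrt(0.25 x 0.75/350 + 0.10 x 0.90/140) = 0.0343
- power = Phi((0.15 - 2.241 x 0.0405)/0.0343) = 95.8%

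The plan states approximately 94%, which is within 2 points. For 12 mg the same method gives more than 99.9%, against a stated figure above 99%.

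**Step 3. Power if a share of every arm is lost with nothing recovered**

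| Loss | 8 mg power |
|---|---|
| 0% | 95.8% |
| 1% | 95.6% |
| 2% | 95.3% |
| 5% | 94.7% |

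Power for 12 mg stays above 99%. Power is not the issue.

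**Step 4. Possible error in the treatment difference**

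The documents give no rate of prohibited-medication use. *Assumption, for illustration only:* a share f of 1% to 5% of each arm leaves under 9.5 after exceptions. In patients that is 2.1 to 10.5 at 12 mg, 3.5 to 17.5 at 8 mg and 1.4 to 7.0 on placebo.

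Let p be the true arm rate (the planned value) and r the true rate among lost patients, with r anywhere from 0 to 0.40 in either arm. If lost patients are imputed at the retained rate:

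- retained rate = (p - f r)/(1 - f)
- arm error = f (p - r)/(1 - f)
- error in the difference = active-arm error minus placebo error

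The maximum has r = 0 on active and 0.40 on placebo. The multiplier of f/(1 - f) is then 0.40 + 0.30 = 0.70 for 12 mg and 0.25 + 0.30 = 0.55 for 8 mg. The minimum has r = 0.40 on active and 0 on placebo. The multiplier is then 0 - 0.10 = -0.10 for 12 mg and -0.15 - 0.10 = -0.25 for 8 mg.

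| f | f/(1 - f) | 12 mg error (points) | 8 mg error (points) |
|---|---|---|---|
| 1% | 0.0101 | -0.10 to +0.71 | -0.25 to +0.56 |
| 2% | 0.0204 | -0.20 to +1.43 | -0.51 to +1.12 |
| 5% | 0.0526 | -0.53 to +3.68 | -1.32 to +2.89 |

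The planned differences are 30 and 15 points. No such calculation is possible for SPRO, because no planned SPRO rate is given.

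**The case against.** The strongest reply is that the intended rule is easy to recover. Section 8.3 is the dedicated withdrawal section, several other sections agree with it, and the Amendment 2 log gives the separation of treatment withdrawal from study withdrawal as its reason for edits that include 8.3. Those entries do not list 9.5, so its sentence was probably just not updated. Strictly, too, 8.3 states follow-up as an intent, and leaving the study also stops treatment, so the clash is over follow-up. Both points are right. But a site reading 9.5 meets an explicit instruction, and nothing tells it to prefer 8.3.

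Second, the affected group may be small. Section 9.5 permits a short steroid course after discussion with the Medical Monitor, and it bars systemic immunosuppressives only as chronic or long-term treatment. Nothing supports the 1% to 5% range, and its largest error needs lost placebo patients to respond at four times the planned rate. This stands: the range is illustrative.

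Third, 9.5 might be meant to keep confounded scores out. Section 12.4.2 names no strategy for starting a hair-active agent, so a placebo patient who regrows hair on another JAK inhibitor would count as a responder. That gap is real. Even so, 8.3 already prescribes continued follow-up for this event, and the prohibited list also contains CYP3A4 inhibitors, CYP3A4 inducers and live vaccines.

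Finally, confounding deviations can be classed as major, and a supportive Per Protocol analysis is planned for both endpoints. That does not recover missing data.

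**Conclusion.** The concern holds. Sections 9.5 and 8.3 give different consequences for the same event, and following 9.5 loses Week 24 outcomes that the primary estimand calls for. Confidence in the textual conflict is high.

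The size is unknown and probably small. The Step 4 ranges rest on an assumed loss and on imputation at the retained patients' rate. They are not bounds, and using baseline and earlier SALT scores in the imputation may shrink the error. The sign changes within the range, and the mixed prohibited list means the documents do not settle the direction of any bias. The case for changing the text rests on contradictory site instructions and avoidable missing data, with SPRO at Week 24 the less protected endpoint. It should be fixed.

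**What to change.** In Section 9.5, make the consequence *discontinuation of study treatment* in place of withdrawal from the study. Keep the short-term-use exception, including its test on confounding of the endpoints. Add a sentence such as: *Scheduled visits, including SALT and SPRO, continue through Week 24 unless the patient withdraws consent.*

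The cost is a sentence or so in an amendment and a communication to sites. Unless it is classed as administrative, the amendment needs IRB/EC approval (Section 13.4) across about 70 sites, so it is best bundled with the next one. It needs no new visits, since 8.3 already intends them, and no new data field or SAP analysis.

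The downside is that some Week 24 scores will be obtained on hair-active prohibited agents, for which Section 12.4.2 names no separate strategy. Those scores can be identified, because medications "taken at the time of the Screening Visit through the Follow-Up Visit will be recorded". Section 8.4 separately directs study withdrawal after emergency unblinding; this change does not touch that rule.
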